10.1.7.5 Sponsor Responsibility for Reporting Adverse Events

All adverse events will be reported to regulatory authorities, IRB or independent ethics committees (IECs), and Investigators in accordance with all applicable global laws and regulations i.e., per ICH Topic E6 (R1) Guidelines for Good Clinical Practice.

10.2 Pharmacokinetic Assessment

10.2.1 Blood Sampling and Processing

For all subjects, blood samples for the determination of MK-7264 will be collected at scheduled time points as delineated in the Study Events Flow Chart ([Section 6](#)).

Instructions for blood sampling, collection, processing, and sample shipment for MK-7264 will be provided separately.

Blood collections outside the following windows will be considered deviations:

Hour	Deviation window
0.0 to 0.5 hour	± 2 minutes
> 0.5 to 2.0 hour	± 2 minutes
> 2.0 to 8.0 hour	± 2 minutes
> 8.0 to 24 hour	± 5 minutes
> 24.0 hour	± 10 minutes

10.2.2 Urine Collection (Part 1 only)

Prior to the predose sample, each subject will be instructed as to urine collection methods.

Urine samples for determination of MK-7264 concentrations will be collected at selected intervals as delineated in the Study Events Flow Chart ([Section 6](#)). For subjects with moderate and severe RI, and subjects with ESRD, urine samples will be collected whenever possible, as they may not be able to produce urine at each interval. For subjects who are anuric, urine samples for urinalysis will not be collected.

On Day 1, a spot collection will be obtained prior to dosing for the pre-dose sample. Subjects will be asked again to empty their bladder within approximately 15 minutes prior to dosing, and no urine will be collected at this time unless it is needed for the pre-dose sample. Only one predose urine sample will be collected on Day 1.

After administration of MK-7264, during the entire postdose in-house observation period, all urine will be collected completely. Urine portions will be pooled per subject within any planned collection interval. Just prior to the end of each sampling interval, subjects will be encouraged to void their bladder again to complete the collection. If they do void at any time during the collection interval, the

time should be documented. Should this be the case, subjects need to attempt to void again at the end of the collection period, as scheduled. However, should subjects be unable to void, this will be documented as well.

Urine will be refrigerated during the collection intervals. The weight of an empty urine collection container and total weight of urine collected during each timed interval will be recorded.

10.2.3 Dialysate Collection

For ESRD subjects only, dialysate samples will be collected at scheduled time points as delineated in the Study Events Flow Chart ([Section 6](#)).

Instructions for dialysate sampling, collection, processing, and sample shipment for MK-7264 will be provided separately.

10.3 Planned Genetic Analysis Sample Collection

Sample collection, storage and shipment instructions for Planned Genetic Analysis samples will be provided in the [Appendix 3](#).

10.4 Future Biomedical Research Samples

The following specimens are to be obtained as part of Future Biomedical Research:

- DNA for future research

10.5 Blood Volume Drawn for Study Assessments

Table 2: Blood Volume Drawn During the Study in Part 1

Sample Type	Number of Time Points	Approximate Volume per Time Point * (mL)	Approximate Sample Volume Over Course of Study (mL)
Screening laboratory safety tests (including hematology, serum chemistry, serology), FSH (for postmenopausal female subjects only) and serum pregnancy (for female subjects only).	1	12.5	12.5
Blood for Planned Genetic Analysis	1	8.5	8.5
On-study hematology and serum chemistry (this includes serum pregnancy for female subjects only when scheduled at the same time)	3	12.5	37.5
Blood for MK-7264	15	3	45
Total Blood Volume (mL)→			103.5 [§]

* Represents the largest collection tube that may be used for this (a smaller tube may be used).

§ If additional safety, or pharmacokinetic, analysis is necessary or if larger collection tubes are required to obtain sufficient plasma/serum for analysis, additional blood may be obtained (up to a maximum of 50 mL).

Table 3 Blood Volume Drawn During the Study in Part 2

Sample Type	Number of Time Points	Approximate Volume per Time Point * (mL)	Approximate Sample Volume Over Course of Study (mL)
Screening laboratory safety tests (including hematology, serum chemistry, serology), FSH (for postmenopausal female subjects only) and serum pregnancy (for female subjects only).	1	12.5	12.5
Blood for Planned Genetic Analysis	1	8.5	8.5
On-study hematology and serum chemistry (this includes serum pregnancy for female subjects only when scheduled at the same time)	6	12.5	75
Blood for MK-7264	58	3	174
Total Blood Volume (mL)→			270 [§]

* Represents the largest collection tube that may be used for this (a smaller tube may be used).

§ If additional safety, or pharmacokinetic, analysis is necessary or if larger collection tubes are required to obtain sufficient plasma/serum for analysis, additional blood may be obtained (up to a maximum of 50 mL).

11 DATA ANALYSIS

11.1 Pharmacokinetic Parameters

11.1.1 Plasma

For all subjects, pharmacokinetic parameters for plasma MK-7264 will be calculated as follows:

AUC0-last:	Area under the concentration versus time curve, from 0 to the time of the last quantifiable (above LLOQ) sample.
AUC0-∞:	Area under the concentration versus time curve from 0 to infinity after dosing.
AUC0-12:	Area under the concentration versus time curve, from 0 to 12 hours after dosing.
AUC0-24:	Area under the concentration versus time curve, from 0 to 24 hours after dosing.
AUC0-48:	Area under the concentration versus time curve, from 0 to 48 hours after dosing.
CL/F:	Apparent clearance after extravascular administration.
C _{max} :	Maximum observed plasma concentration after the administration of a given dose.
T _{max} :	Time to maximum observed plasma drug concentration.
t _{1/2} :	(Apparent) terminal half-life.
V _d /F:	Apparent volume of distribution during the terminal phase

No value for AUC0-∞, CL/F, V_d/F, or apparent terminal t_{1/2}, will be reported for cases that do not exhibit a terminal log-linear phase in the concentration versus time profile.

No pharmacokinetic parameters will be calculated for subjects with 2 or fewer consecutive time points with detectable concentrations.

Individual and mean plasma concentration time curves (both linear and log-linear) will be included in the final report.

11.1.2 Urine (Part 1 and Part 2)

For subjects with moderate or severe renal impairment, subjects with ESRD, and for matched healthy subjects, pharmacokinetic parameters for urine MK-7264 will be calculated as follows:

Ae0-24:	Total amount of drug excreted unchanged in the urine over the period of 24 hours, obtained by adding the amounts excreted over each collection interval.
---------	--

Ae0-48: Total amount of drug excreted unchanged in the urine over the period of 48 hours, obtained by adding the amounts excreted over each collection interval.

CLr: Renal clearance calculated as $Ae(t'-t'')/AUC(t'-t'')$ where $t'-t''$ is the longest interval of time during which Ae and AUC are both obtained.

Fe: Fraction of MK-7264 excretion during each collection interval. Obtained by dividing the amount of MK-7264 excreted in each collection interval by the dose.

11.1.3 Hemodialysis: Dialysate and Plasma

For subjects with ESRD only, pharmacokinetic parameters for plasma MK-7264 will be calculated as follows based on concentration in plasma samples from the pre-dialyzer line during the dialysis period (Ca) and on concentration in plasma samples from the post-dialyzer line during the dialysis period (Cv):

AUCD: Plasma AUC values determined from Ca versus time profile during the dialysis period (2-6 hours) using 'linear up, log down' calculation method option in WinNonlin.

AUC(2.5-6)Ca: Plasma AUC values determined from Ca versus time profile during the dialysis period from 2.5 hour to 6 hours using 'linear up, log down' calculation method option in WinNonlin.

AUC(2.5-6)Cv: Plasma AUC values determined from Cv versus time profile during the dialysis period from 2.5 hour to 6 hours using 'linear up, log down' calculation method option in WinNonlin.

CLD,plasma: Dialysis clearance based on plasma, calculated as $Q \times R \times [AUC(2.5-6)Ca - AUC(2.5-6)Cv] / AUC(2.5-6)Ca$, where Q is the flow rate of blood through the dialyzer, and R is the ratio of blood drug concentration to plasma drug concentration

For subjects with ESRD only, pharmacokinetic parameters for dialysate MK-7264 will be calculated as follows:

CD: Concentration in dialysate samples.

AD: Amount of drug recovered from each dialysate collection, calculated as:
 $CD \times \text{dialysate volume}$

rr: Rate of drug removal, calculated as: $(CD \times \text{dialysate flow rate})$

AD, total: Cumulative amount of drug recovered from the dialysate will be obtained by integrating the rr versus time profile over the dialysis session duration, using actual times relative to the start time of dialysis.

CLD,dialysate: HD clearance based on dialysate, calculated as: $AD,\text{total}/AUCD$.

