10.1.5 Hemodialysis (ESRD Subjects Only)

ESRD subjects only will receive HD as per their regular schedule. Dosing in Period 1 will occur immediately following completion of a normally scheduled HD and dosing in Period 2 will occur approximately 2 hours prior to the normally scheduled HD as per the Study Events Flow Chart ([Section 6](#)).

In Period 2, the HD period will be approximately 4 hours for all subjects. Blood samples collected during HD will be collected from both the pre-dialyzer and post-dialyzer blood lines.

The blood flow, dialysate flow, and the make and model of the dialyzer will be recorded.

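### CLD,plasma has no ultrafiltration term and ultrafiltration is not among the recorded dialysis settings, so this clearance is understated whenever net fluid is removed

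*Protocol*

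**What the plan says.** Protocol section 11.1.3 defines CLD,plasma as Q × R × [AUC(2.5-6)Ca − AUC(2.5-6)Cv] / AUC(2.5-6)Ca. Ca and Cv are plasma concentrations in the pre-dialyzer and post-dialyzer lines, and R is the blood-to-plasma ratio of drug concentrations. Only one flow appears: "where Q is the flow rate of blood through the dialyzer".

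On the dialysate side the same section gives:

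- rr is CD × dialysate flow rate, under the label "Rate of drug removal, calculated as". It does not say whether this is the flow entering or leaving the dialyzer.
- AD is CD × dialysate volume for each collection.
- AD,total comes from rr: "Cumulative amount of drug recovered from the dialysate will be obtained by integrating the rr versus time profile".
- CLD,dialysate is AD,total divided by AUCD.

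Section 10.1.5 lists what is kept from the dialysis session: "The blood flow, dialysate flow, and the make and model of the dialyzer will be recorded". Ultrafiltration rate or volume is not listed. The Period 2 flow chart in section 6.2 has no weight row.

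Extent of removal by HD is a Part 2 primary objective (section 8.1.1), and section 7.2.3 names CLD,plasma, CLD,dialysate, AD and AD,total as its measures. Section 8.1.3 puts the same four under an exploratory objective, section 8.2 lists them after the primary endpoints, and section 11.2.3.3 plans only listings and descriptive statistics for them. The modelled evaluation of removal (protocol 11.2.3.3, SAP 9.8.3) is the HD/non-HD ratio of AUC0-∞, AUC0-last, Cmax and CL/F.

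**The concern.** A dialysis session may remove fluid as well as solute. If it does, less blood leaves the dialyzer than enters it, and the fluid that has left carries drug with it. A formula that applies the inlet flow to both lines credits the outlet with drug that has already gone into the dialysate, so the clearance comes out low.

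The direction is fixed, and the error is relatively largest when extraction is low, which is when the question of whether dialysis removes a meaningful amount is closest. In the limiting case Cv = Ca, the planned formula returns zero clearance although drug is leaving at a clearance equal to UF. With neither UF nor scheduled pre- and post-dialysis weights in Period 2, the correction could not be made from the data that the protocol schedules.

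**Working it through.** The documents state no clearance, extraction, flow or UF value, so there is no figure of the plan to reproduce. The check is a mass balance, followed by a range under stated assumptions.

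**Plasma side.** Let E = (AUC Ca − AUC Cv) / AUC Ca over 2.5-6 h, and treat flows as constant over the session.

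- Drug in: Q × R × Ca.
- Drug out in the blood line: (Q × R − UF) × Cv. The term in UF has no R because ultrafiltrate is cell-free and leaves from plasma. This holds whether or not drug also sits in red cells, provided it equilibrates between cells and plasma.
- True clearance: Q × R × E + UF × (1 − E), where 1 − E = AUC Cv / AUC Ca.
- Planned clearance: Q × R × E.
- Understatement: UF(1 − E) / [Q × R × E + UF(1 − E)]. It is zero if UF = 0 and positive if UF > 0 and E < 1.

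**Assumed inputs (none is in the documents).** Q 300-400 mL/min; R 0.65-1.0; UF 4-12.5 mL/min, which is about 1 to 3 L over the planned session of about 4 h (1,000/240 = 4.2; 3,000/240 = 12.5).

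| E | Smallest (Q 400, R 1.0, UF 4) | Largest (Q 300, R 0.65, UF 12.5) |
|---|---|---|
| 0.1 | 3.6/(40 + 3.6) = 8.3% | 11.25/(19.5 + 11.25) = 36.6% |
| 0.2 | 3.2/(80 + 3.2) = 3.8% | 10/(39 + 10) = 20.4% |
| 0.3 | 2.8/(120 + 2.8) = 2.3% | 8.75/(58.5 + 8.75) = 13.0% |
| 0.5 | 2/(200 + 2) = 1.0% | 6.25/(97.5 + 6.25) = 6.0% |

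A mid-range case: Q 300, R 1.0, UF 10, E 0.1 gives 30.0 mL/min planned against 30.0 + 9.0 = 39.0 mL/min, 23% low.

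**Why R must stay out of the added term.** At Q 300, R 0.65, UF 12.5 and E 0.1, the true value is 30.75 mL/min. Adding UF × R × (1 − E) instead gives 19.5 + 7.3 = 26.8 mL/min, still 13% low. The two versions agree only at R = 1.

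**Dialysate side.** Spent-dialysate flow is inlet flow Qd plus UF. If rr uses inlet flow, rr, AD,total and CLD,dialysate are low by UF/(Qd + UF). At an assumed Qd of 500-800 mL/min this runs from 4/804 = 0.5% to 12.5/512.5 = 2.4%. If rr uses outlet flow, it is zero. AD per collection is likewise unbiased if the volume is the measured spent volume.

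**Modelled ratios.** AUC0-∞, AUC0-last, Cmax and CL/F come from plasma concentrations and dose. No Q, R, dialysate flow or UF enters them.

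**The case against.** The strongest reply is that the modelled evaluation of removal does not use the dialyzer formulas at all. The flow-based measures are summarised descriptively in six subjects and sit under an exploratory objective. The documents do not say that net fluid is removed, or how much. They give no extraction ratio either, so the upper end of the range rests on an assumption that extraction is low. UF may also be held in routine dialysis records or covered elsewhere: "Instructions for dialysate sampling, collection, processing, and sample shipment for MK-7264 will be provided separately".

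Most of this stands, and it limits the point in three ways.

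- A reader might infer that the Part 2 primary objective is biased low. The documents do not support that: the HD/non-HD ratios are untouched, and none of the Part 2 primary endpoints in section 8.2 uses a flow.
- A reader might infer that dialysate recovery is also always low. That depends on an undefined term; with outlet flow there is no bias.
- A reader might attribute any gap between the two clearances to UF. They also use different windows (2.5-6 h for CLD,plasma, 2-6 h for AUCD), so UF is not the only possible cause.

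The reply does not remove the fault in CLD,plasma. Section 7.2.3 presents that parameter as a measure of removal, and its formula is wrong in a known direction whenever UF is above zero. Nor is small size a full answer: SAP section 9.9 checked missing dialysate samples and reported an effect on extent of removal of no more than 1%, so effects of a few percent were thought worth checking.

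**Conclusion.** The point holds as a minor, inexpensive improvement confined to the flow-based measures. CLD,plasma is understated whenever net UF is above zero, by UF(1 − E) / [Q × R × E + UF(1 − E)]. Under the assumed flows, R and UF this is about 8-37% at E = 0.1, 4-20% at 0.2, 2-13% at 0.3 and 1-6% at 0.5. AD,total and CLD,dialysate are low by about 0.5-2.4%, conditional on inlet flow being used. The direction follows from the protocol's own formula; the size rests wholly on assumed values, and with no fluid removal there is no bias. The conclusion on removal drawn from the AUC, Cmax and CL/F ratios is not affected.

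**What to change.** - Section 10.1.5: add net ultrafiltration volume and session duration to the recorded items.
- Section 11.1.3, CLD,plasma: add UF × AUC(2.5-6)Cv / AUC(2.5-6)Ca, without R.
- Section 11.1.3, rr and AD: define the flow and the volume as total spent dialysate (inlet flow plus UF).
- For the completed study: retrieve UF from the dialysis records if it is there. If not, report CLD,plasma as a lower bound with respect to UF, and say the same of CLD,dialysate and AD,total only if inlet flow was used.

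The cost is one more machine reading per session and a small change to the formulas. No extra sample or procedure is needed, and the modelled analysis does not change.

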11.2 Statistical Methods

The statistical analysis of the data obtained from this study will be the responsibility of the Data Management and Biometrics department at Celerion.

If, after the study has begun, changes are made to the statistical analysis plan stated below, then these deviations to the plan will be listed, along with an explanation as to why they occurred, in the Clinical Study Report (CSR).

Additional statistical analyses, other than those described in this section, may be performed if deemed appropriate.

11.2.1 Determination of Sample Size

The sample size selected for each population to evaluate the effect of renal impairment on the PK of MK-7264 was not chosen to satisfy any a priori statistical requirement. This sample size (N= 6 per group) has historically been shown to be sufficient for studies of this type and should provide adequate data to support the planned analyses. Nevertheless, estimates of the expected precision of the estimates, based on these sample sizes are presented below.

The precision of the estimated ratios of geometric means (severe renal impairment / normal renal function) of pharmacokinetic parameters obtained from this study can be assessed by calculating the half-width of the 90% confidence intervals expected for the given sample size and assumed variability. The between-subject geometric coefficient of variation (GCV) for MK-7264 AUC0-12, after administration of 50 mg MK-7264 observed in healthy subjects in a previous study (PN 022) is 15%. Since the between subject variability in severe renal subjects has historically been seen to be 2-3 folds higher in many studies, the geometric CV obtained from healthy were inflated by a factor of 2 for severe renal subjects and was used for the following calculations. Assuming a sample size of 6 subjects per population and observed pooled between-subject standard deviation of 0.21 for AUC0-12 on the natural log scale, then the half width of the 90% confidence intervals of GMRs for MK-7264 AUC0-12 on the log scale will be 0.22. The lower and upper 90% confidence limits for the true GMRs will be given by $OBS/1.25$ and $OBS*1.25$ for AUC0-12, respectively, where OBS is the observed GMR. Thus, for example, if the observed GMR for AUC0-12 was 1.50, then the 90% confidence intervals for the GMR would be 1.20 to 1.87.

Table 4: Estimated Precision Calculations

Parameter	N (per group)	Half width (log scale)	Observed GMR	90% confidence interval for Observed GMR
AUC0-12	6	0.22	1.50	(1.20, 1.87)
Cmax	6	0.24	1.50	(1.18, 1.91)

Note: GCV for AUC0-12 and Cmax on Day 1 from PN 22 for 50 mg bid dose were 15% and 16%, respectively

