Additionally, plots of MK-7264 pharmacokinetic parameter values AUC_{0-∞}, AUC_{0-last}, C_{max}, CL/F, and CL_r versus eGFR along with a regression line and 95% confidence bands for regression line will be constructed. Different symbols will be used to identify different renal function groups. Additionally, separate plots of AUC_{0-∞} and C_{max} values vs age and body weight will be provided

Individual values will be listed for each PK parameter (AUC_{0-∞}, AUC_{0-last}, AUC₀₋₁₂, AUC₀₋₂₄, AUC₀₋₄₈, C_{max}, T_{max}, CL/F, V_z/F, apparent terminal t_{1/2}, A_{e0-24}, A_{e0-48}, and F_e) by population, and the following (non-model-based) descriptive statistics will be provided: N (number of subjects with non-missing data), arithmetic mean, standard deviation, arithmetic percent CV (calculated as 100 x standard deviation/ arithmetic mean), median, minimum, maximum, geometric mean, and geometric percent CV (calculated as 100 x sqrt(exp(s²) - 1), where s² is the observed variance on the natural log-scale).

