11.2.3.2 Secondary Analysis: Categorical Analysis

Separately for each pharmacokinetic parameter, individual values of AUC_{0-∞}, AUC_{0-last}, C_{max}, CL/F, and CL_r (as appropriate) will be natural log-transformed and evaluated with a linear fixed-effects model containing a categorical effect for population (ESRD renal impairment Period 1 of Part 2, severe RI, moderate RI, and healthy matched control, based on BSA normalized eGFR). The REPEATED statement with the GROUP=Population option will be used in SAS PROC MIXED to estimate separate variances for each population. The Kenward and Roger adjustment will be used to calculate the denominator degrees of freedom for the fixed-effect (DDFM=KR). Ninety-five percent (95%) confidence intervals for the least squares means for each population will be constructed on the natural log scale and will reference the t-distribution. Exponentiating the least-squares means and their corresponding 95% confidence intervals will yield estimates for the population geometric means and confidence intervals about the geometric means on the original scale. Sample SAS code is given below:

```
Proc mixed =data;
CLASS Population Subject;
MODEL lnPk = Population / DDFM=KR;
REPEATED / GROUP=Population;
LSMEANS Population / CL;
run;
```

To compare subjects with RI in each of the renal categories to subjects with normal renal function, a two sided 90% confidence interval for the true difference in means (renal impairment – normal renal function) will be calculated for each PK parameters (AUC_{0-∞}, AUC_{0-last}, C_{max}, CL_r, and CL/F) using the mean square error from the model and referencing a t-distribution. For each of the RI populations, these confidence limits will be exponentiated to obtain the 90% confidence interval for the true ratio of geometric means (renal impairment/normal renal function) for each pharmacokinetic parameter.

Figures showing individual pharmacokinetic values with GMs (95% confidence intervals) by population, plotted on the natural log scale, will be provided for AUC_{0-∞}, AUC_{0-last}, Cmax, CL/F, and CL_r.

Summary Statistics using BSA un-normalized eGFR: The subjects will be re-categorized into different renal categories based on their BSA un-normalized eGFR and non-model based summary statistics by population will be provided for (AUC_{0-∞}, AUC_{0-last}, AUC₀₋₁₂, AUC₀₋₂₄, AUC₀₋₄₈, Cmax, Tmax, CL/F, Vz/F, apparent terminal t_{1/2}, Ae₀₋₂₄, Ae₀₋₄₈, and Fe, as applicable).

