9.8.2 Determination of Sample Size and Power to Address Study Hypotheses

Refer to the protocol [16.1.1.4].

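### The stated variability assumption (healthy CV doubled for severe RI) gives a pooled SD of 0.233, not the 0.21 behind the precision figures in Protocol 11.2.1

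*Protocol*

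**What the plan says.** Protocol 11.2.1 says that the sample size "was not chosen to satisfy any a priori statistical requirement" and then offers expected precision for the severe/normal comparison. Its inputs are these:

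- **Healthy variability.** The note under Table 4 reads "GCV for AUC0-12 and Cmax on Day 1 from PN 22 for 50 mg bid dose were 15% and 16%, respectively".
- **Inflation for severe RI.** The reason given is "Since the between subject variability in severe renal subjects has historically been seen to be 2-3 folds higher in many studies", and the action taken is that "the geometric CV obtained from healthy were inflated by a factor of 2 for severe renal subjects and was used for the following calculations".
- **SD used.** The next sentence assumes 6 subjects per population and an "observed pooled between-subject standard deviation of 0.21 for AUC0-12 on the natural log scale". No SD is printed for Cmax.
- **Results.** Table 4 gives log-scale half-widths of 0.22 (AUC0-12) and 0.24 (Cmax). At an observed GMR of 1.50 the 90% intervals are 1.20 to 1.87 and 1.18 to 1.91. The text gives the AUC0-12 limits as the observed GMR divided and multiplied by 1.25.

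SAP 9.8.2 adds nothing on sample size and points back to the protocol.

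**The concern.** A reader who follows the inflation sentence does not arrive at 0.21. The section therefore carries two variability assumptions, and it is unclear which one lies behind Table 4. This matters because 11.2.1 holds the only quantitative statement of the precision expected from 6 per group for severe RI against normal. If the doubled CV is the real assumption, the printed intervals are too narrow. If 0.21 is, the text misreports how much extra variability was allowed for in severe RI.

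**Working it through.** **Inputs.** Healthy geometric CV 15% (AUC0-12) and 16% (Cmax); factor 2 for severe RI, hence 30% and 32%; 6 per group; 90% two-sided interval (all Protocol 11.2.1). Protocol 11.2.3.1 defines geometric CV as 100 × sqrt(exp(s²) − 1), where s² "is the observed variance on the natural log-scale", so s = sqrt(ln(1 + CV²)). Section 11.2.1 does not name the quantile. Protocol 11.2.3.2 plans the same 90% interval "using the mean square error from the model and referencing a t-distribution", so t is used here, with 6 + 6 − 2 = 10 df: t(0.95, 10) = 1.8125.

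**Formulas.** Pooled SD = sqrt((s_healthy² + s_severe²)/2). Half-width = t × SD × sqrt(2/6). Limits = 1.50 × exp(± half-width).

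**Step 1: the plan's own figure, starting from 0.21.** Half-width = 1.8125 × 0.21 × 0.5774 = 0.2197, which rounds to 0.22; exp(0.22) = 1.246; interval 1.204 to 1.869. Everything from 0.21 onward is consistent with the print. A normal quantile (1.645) would give 0.199, so the printed step from 0.21 to 0.22 also points to t on 10 df.

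**Step 2: starting from the stated CVs.**

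| | AUC0-12 | Cmax |
|---|---|---|
| Log SD, healthy | 0.1492 | 0.1590 |
| Log SD, severe (CV doubled) | 0.2936 | 0.3122 |
| Pooled SD | 0.2328 | 0.2478 |
| Half-width, t on 10 df | 0.2436 | 0.2593 |
| Printed half-width | 0.22 | 0.24 |
| Ratio to printed | 1.107 | 1.080 |
| Interval at GMR 1.50 | 1.176 to 1.914 | 1.157 to 1.944 |
| Printed interval | 1.20 to 1.87 | 1.18 to 1.91 |

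**Step 3: can rounding explain it?** No.

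- A healthy CV anywhere from 14.5% to 15.5% gives a pooled SD of 0.225 to 0.240.
- A pooled SD that prints as 0.21 (0.205 to 0.215) needs a healthy CV of 13.2% to 13.8%.
- At a healthy CV of 15%, it needs an inflation factor of 1.68 to 1.80 rather than 2.
- A Cmax half-width that prints as 0.24 needs a healthy CV of 14.4% to 15.1%, against the stated 16%.

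**Step 4: what does reproduce the print?** Doubling the log-scale *variance* in both groups does. Tripling it in severe subjects only is equivalent, since (1 + 3)/2 = 2.

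- AUC0-12: SD = sqrt(2) × 0.1492 = 0.211, half-width 0.221, interval 1.203 to 1.871 (1.8705 before rounding to three decimals), which prints as 1.20 to 1.87 within rounding.
- Cmax: SD = sqrt(2) × 0.1590 = 0.225, half-width 0.235. The printed interval 1.18 to 1.91 follows from the rounded 0.24 (1.180 to 1.907).

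Doubling the variance in severe subjects only gives SD 0.183 and half-width 0.191, which do not match. The text describes neither of the matching routes.

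**The case against.** The strongest reply is that 11.2.1 leaves two choices open, and that other choices keep the doubled CV and still come close to Table 4.

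- **Normal quantile.** The doubled CV with 1.645 gives half-widths of 0.221 and 0.235, which round to Table 4. But the pooled SD remains 0.233, so the printed 0.21 would still be wrong. This route also conflicts with the t reference in 11.2.3.2 and with the printed step from 0.21 to 0.22.
- **Pooling all three Part 1 groups, with only severe inflated.** This gives SD 0.209 and, with t on 10 df, a half-width of 0.218 for AUC0-12; both round to the print. For Cmax at 16% it gives 0.232, which prints as 0.23; only an unrounded CV of about 16.2% or more reaches 0.24. It also joins a three-group error term, which carries 15 df, to a 10-df quantile. With 15 df the half-widths are 0.211 and 0.225, and neither matches. It fits poorly with a severe/normal comparison and with the separate variances per population planned in 11.2.3.2.

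What stands is that the replacement half-widths depend on pooling two groups and on t with 10 df, and that the print does not identify the source of the mismatch. It also stands that the stakes are low: N does not rest on the calculation, AUC0-12 is an exploratory parameter (Protocol 8.1.3), and SAP 9.8.3.3 reports that no hypotheses were tested.

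**Conclusion.** The concern holds. Doubling the healthy CV for severe RI gives a pooled SD of 0.233 for AUC0-12, outside anything that rounds to 0.21, and half-widths of 0.244 and 0.259 against the printed 0.22 and 0.24. The SD result needs only the protocol's own CV definition and equal pooling of the two groups compared; the half-widths also need t on 10 df.

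Which statement is wrong cannot be settled from the documents. If the doubled CV is meant, the intervals are about 11% (AUC0-12) and 8% (Cmax) wider on the log scale than stated. If 0.21 is meant, no figure in Table 4 changes and the inflation sentence is the error. In either case this is a reporting inconsistency of small consequence: no decision rule, sample size or analysis depends on it.

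**What to change.** Reconcile the two statements in Protocol 11.2.1, naming the groups pooled and the quantile used.

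- **If the doubled CV in severe RI is intended:** state pooled SDs of 0.23 (AUC0-12) and 0.25 (Cmax). Give half-widths of 0.24 and 0.26 (t on 10 df, from the unrounded SDs 0.2328 and 0.2478) and AUC0-12 limits of the observed GMR divided and multiplied by 1.28. The Table 4 intervals become (1.18, 1.91) and (1.16, 1.94).
- **If 0.21 is intended:** replace the inflation sentence with the assumption actually used (for example, log-scale variance doubled), print the SD used for Cmax, and leave Table 4 as it stands.

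The cost is a text correction, with Table 4 under the first option, where the stated precision becomes slightly less favourable. N stays at 6 per group, and nothing changes in the analyses or conduct.
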